	what time periods the differences are most pronounced. We will model processing speed as a function of dose and day of study and will allow differences between dose groups to vary as a function of time through a series of interaction terms. The primary analysis will consider three key time periods, Days 3-6, 7-10 and 11-14 when we expect differences in processing speed between the BCAA-treated groups and placebo to be largest. Likelihood ratio tests will be employed to specifically test whether there are differences in mean processing speed between placebo and any of the BCAA doses at the three key time periods.
Data And Safety Monitoring Plan	The investigators will be responsible for data quality management and ongoing assessments of safety. An experienced neurologist, [name] will act as the Independent Medical Monitor for this study.

Evaluation	Screening Day 0	Treatment Phase Days 0 – 21
Informed Consent/Assent Review Inclusion/Exclusion Criteria Pregnancy Test on Post-Menarchal Females	X	×
Demographics Concussion History Randomization		Х
Axon Sports CCAT		Daily
Clinical Symptom Checklist		Daily
Cognitive and Physical Activity Assessments		Daily
Sleep Assessment		Daily
Drug Accountability Assessment		Daily
Actigraphy		Continuous
Computerized Dynamic Posturography (Optional)		Days 0-4, 5-9, 12-16
Adherence Assessment		Days 0, 5-9, 12-16
Adverse Event Assessment		Days 5-9, 12-16, 22-24

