## 4.2 Allocation to Treatment Groups and Blinding

The study biostatistician, [name], will generate a randomization schedule for implementation in the randomization module of the study database system. The randomization scheme will be based on an equal allocation of each of the possible doses or placebo, and stratified based on sex. The randomization schedule is uploaded into the data management system (DMS) and provided to the Investigational Drug Service (IDS). The IDS will use the randomization schedule to prepare kits of BCAA doses or placebo for distribution. Upon confirmation of eligibility, the DMS will provide study personnel with a number that is then given to the IDS and corresponds to the kit number to be distributed. All study team members will be blinded to treatment assignment. The Database Administrator will have access to the link between the kit number and the treatment arm and will provide this information to the Investigational Drug Service (IDS) so that kits are prepared according to this scheme. BCAA and placebo treatment kits will appear identical.

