		Computerized balance testing (optional)* Distribute actigraphy sleep monitor Distribute study drug	
Days 0-21	Daily assessments via study website	Computerized cognitive testing Clinical symptom checklists Cognitive & physical activity assessments Sleep assessment	15 minutes
Visit 2, Day 5-9	Routine Visit	Computerized balance testing (Optional) Compliance urine test	20 minutes
Visit 3, Day 12-16	Routine Visit	Computerized balance testing (Optional) Compliance urine test	20 minutes
Visit 4, Day 22-24	End of Study	Return used and unused drug bottles Return actigraphy monitor	10 minutes

\* - If enrollment occurs on a Saturday or Sunday, balance testing can be conducted the following Monday or Tuesday.

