## 7.3.2 Primary Efficacy Analysis

The primary intent to treat analysis will include all subjects who enroll and contribute at least 10 days of data to the study. The mean trajectory in decline and recovery in processing speed is unknown. Thus the primary analysis will aim to determine whether there are differences in processing speed between the BCAA dose groups and placebo, and if so, at what time periods the differences are most pronounced. The primary analysis will focus on results for the first 10 days of the study when we anticipate that the majority of subjects will be highly compliant. We will model processing speed as a function of dose and day of study and will allow differences between dose groups to vary as a function of time through a series of interaction terms. To ensure that the number of interaction terms does not become too large, we will consider groups of two to four time points, looking specifically at whether

04/06/2018 V 0.16

there are differences between any of the dose groups and placebo at Days 1-2, 3-6, 7-10, 11-14, 15-18, 19-21. The primary analysis will consider three key time periods, Days 3-6, 7-10 and 11-14 when we expect differences in processing speed between the BCAA-treated groups and placebo to be largest. Since processing speed differs with age, the model will be adjusted for age to account for any imbalances in age between dose groups. A mixed effects model will be used to account for correlations between repeated measurements on individual subjects. Likelihood ratio tests will be employed to specifically test whether there are differences in mean processing speed between placebo and any of the BCAA doses at the three key time periods. These three global tests will be conducted at a family-wise error rate of 0.05, using a Bonferroni correction to account for the three individual global tests. If statistical significance is achieved for the global test, we will then compare individual dose levels to placebo within time periods, again using a correction for four multiple tests per key time period.

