#### 7.3.3 Analysis of Secondary Endpoints

Secondary endpoints, including clinical symptoms such as the posturography and sleep assessments, and the learning, attention and working memory components of the neurocognitive battery will be modeled using a similar approach as described above for the primary efficacy analysis (Section 7.3.2), with the goal of assessing differences between groups over time, after adjustment for age differences. We will assess the distribution of the outcome and either use a transformation to achieve approximate normality or use a generalized mixed effects model. Time to event outcomes (e.g. time to return to school or sports participation) will be modeled using a Cox proportional hazards model. We will secondarily adjust our primary models for body mass index (BMI) and compliance to obtain information on whether individuals with lower BMI, and presumably higher BCAA/kg dosing have better outcome.

We will also monitor compliance including adherence to treatment and daily completion of neurocognitive testing. It is of interest to determine whether there are differences in compliance among the dosage groups versus placebo whether compliance decreases as a function of time, and whether compliance differs among groups over time. Adherence to treatment is measured in terms of number of bottles of consumed per day (0, 1, or 2) and will be modeled as an ordinal outcome. Adherence to treatment will be assessed using generalized estimating equations (GEE) models as we have repeated measures on adherence for each subject across all time points in the study and are primarily interested in differences between groups. In particular we anticipate that with regular prompting and encouragement, subjects will consistently complete their neurocognitive functioning tests up until about 10 to 14 days into the study. We anticipate that compliance may begin to decrease around the 10 to 14 day point as subjects begin to feel better and return to their normal routines. Assessment of compliance will be key information needed to design the anticipated pivotal trial of subsequent research studies.

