## 7.4 Sample Size and Power

The primary analysis of the processing speed data is broadly based, reflecting the fact that that this is a feasibility study in which we have limited knowledge regarding the temporal patterns of decline and recovery in human neurocognitive functioning following concussion. We hypothesize that BCAA-treated groups will differ from placebo at specific time periods. The power calculation is based on comparisons of each dose group to placebo at each of the key time periods. These time periods each encompass three daily measurements per subject. With 10 subjects per dose group, and three repeated measurements per subject we have 80% power to detect mean differences in processing speeds between the BCAA group and the placebo group on the order of 0.122 seconds. Putting this in the context of a mean processing speed for healthy individuals of ages 14 to 34 of 2.46 to 2.51 seconds (Axon Sports unpublished), means that detectable differences between groups are on the order of 5% of the mean of a healthy individual. The analysis is based on a standard deviation in healthy individuals of 0.08, which we inflated to 0.10 based on our experience with injured or sick subjects, where variances are generally larger than their healthy counterparts. The intra-class correlation coefficient was set to 0.5. The calculation assumes a two-sided family-wise Type I error rate of 0.05 and uses a Bonferroni correction with four contrasts for each time period. The overall sample size is thus 50 subjects. We will consider a subject who contributes data up until and including at least Day 10 to be "evaluable for efficacy." We conservatively anticipate that no more than 72 subjects will be enrolled in order to achieve 50 evaluable subjects. We anticipate that it will take us approximately 12-18 months to recruit these subjects.

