## **10 STUDY ADMINISTRATION**

## **10.1 Treatment Assignment Methods**

#### **10.1.1 Randomization**

The study biostatistician, [name], will generate a randomization schedule that will be implemented in the randomization module of the study database system. The randomization scheme will be based on equal allocation of BCAA's to placebo and stratified based on sex. Upon confirmation of eligibility in the DMS, the randomization module will be programmed to generate a randomization number that corresponds to a unique kit number of BCAA or placebo treatment. This kit number will be used to distribute treatment.

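### The primary model adjusts only for age: it omits the randomisation stratifier (sex) and any Day 0 processing-speed score, and the precision gain from Day 0 is conditional and may be close to zero

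*Combined protocol and SAP*

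**What the plan says.** Section 7.3.2 models processing speed on dose, grouped study day and their interactions, with a mixed model for repeated measurements. The only covariate is age: "Since processing speed differs with age, the model will be adjusted for age to account for any imbalances in age between dose groups". The day groups begin at Days 1–2, and the primary tests use Days 3–6, 7–10 and 11–14.

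Section 4.2 describes the allocation: "The randomization scheme will be based on an equal allocation of each of the possible doses or placebo, and stratified based on sex". Section 10.1.1 repeats that it is equal allocation of BCAA "to placebo and stratified based on sex". Sex does not return as a model term. Section 7.3.2 names gender only as something to relate to missing data, and Section 7.3.3 extends the models by two other variables: "We will secondarily adjust our primary models for body mass index (BMI) and compliance".

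Table 1 has a row for "Axon Sports CCAT", marked daily under a treatment phase of Days 0–21. The visit table in Section 5.2 has a Days 0–21 row, "Daily assessments via study website", which includes cognitive testing. The primary model gives a Day 0 score no role.

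Section 7.4 plans on an SD of 0.10, 10 subjects per group, three repeats, 80% power, four Bonferroni-corrected contrasts per period and no covariate: "The intra-class correlation coefficient was set to 0.5". The stated detectable difference is 0.122 s.

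**The concern.** Two terms that one would expect in this model are absent. The first is the stratification factor: a design that balances on sex is normally analysed with sex in the model, so that the standard errors reflect the balance that was built in. The second is a baseline value of the outcome itself, usually the most useful covariate in a repeated-measures trial.

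Precision is what is at stake. With about 10 evaluable subjects per arm and corrected contrasts, a pre-dose score on the same test could narrow the comparisons at almost no cost. Section 7.3.2 itself names maintaining power as an aim, and it already accepts covariate adjustment in principle.

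**Working it through.** **Inputs (Section 7.4).** SD 0.10; ICC 0.5; m = 3 repeats; n = 10 per arm; two-sided alpha 0.05/4 = 0.0125; 80% power.

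**Reproducing 0.122 s.** The variance of a subject's window mean, as a share of SD², is v = ICC + (1 − ICC)/m = 0.5 + 0.5/3 = 0.667. The detectable difference is (2.498 + 0.842) × 0.10 × √(2 × 0.667/10) = 0.122 s. The plan's figure is therefore a calculation with no covariate at all, not even age.

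**Adding Day 0 to an age-adjusted model.** Assumptions: every subject has a scored pre-dose Day 0 test; its correlation with each later score equals the ICC, 0.5; age explains a share f of between-subject variance. The documents give no value for f, so a range is shown.

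- Window-mean variance after age: v(f) = 0.5(1 − f) + 0.5/3
- Day 0 variance after age: b(f) = 0.5(1 − f) + 0.5
- Covariance after age: c(f) = 0.5(1 − f)
- Share of window-mean variance removed by Day 0: R² = c²/(v × b)

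For f = 0.2: v = 0.567, b = 0.9, c = 0.4, so R² = 0.16/0.51 = 0.314. Age only gives 3.340 × 0.10 × √(2 × 0.567/10) = 0.112 s. Age plus Day 0 gives 0.112 × √(1 − 0.314) = 0.093 s.

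| Age share f (assumed) | Age only | Age + Day 0 | Effective n per arm, from 10 |
|---|---|---|---|
| 0 | 0.122 s | 0.096 s | 16.0 |
| 10% | 0.117 s | 0.095 s | 15.3 |
| 20% | 0.112 s | 0.093 s | 14.6 |
| 30% | 0.107 s | 0.091 s | 13.9 |
| 50% | 0.096 s | 0.086 s | 12.5 |

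Effective n is 10/(1 − R²), relative to the age-only model on the same row.

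**Sensitivity, with age explaining nothing.**

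- Day 0 correlation of 0.4, 0.3 or 0.2 in place of 0.5: 0.122 s falls only to 0.106, 0.113 or 0.118 s.
- Half of the Day 0 scores unusable, correlation 0.5: effective n = 10 × (0.5/0.625 + 0.5) = 13.0.
- Four repeats, matching the four-day windows: 0.118 to 0.091 s.
- t critical values, with the covariate charged one degree of freedom: 0.126 to 0.101 s.
- Change from Day 0 as the outcome: variance share 0.667 + 1 − 2 × 0.5 = 0.667, so there is no gain. The score has to enter the model; subtracting it does not help.

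**Pessimistic assumptions stacked.** Take f = 0.5, a Day 0 correlation of 0.3 and half of the scores unusable. With one common age slope, age accounts for 0.25 of the 0.30 covariance and leaves 0.05. Then R² = 0.05²/(0.417 × 0.75) = 0.008, and effective n = 10 × (0.5/0.992 + 0.5) = 10.04, a gain of about 0.04 subjects per arm.

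**Sex.** The documents give no variance explained by sex, so no gain can be computed.

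**Does a scored Day 0 test exist?**

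- For: Table 1 and the Section 5.2 visit table both place daily cognitive testing in Days 0–21, which is 22 days.
- Against: Section 7.3.2 counts 21 time points and starts its windows at Day 1. The Visit 1 procedures in Section 5.2 name no CCAT. Section 10.7 pays up to $50 for complete data entry, and 21 × $1 + 7 × $2 + 3 × $5 = $50 fits 21 entry days; a 22nd would make $51.
- Open: Section 6.2.1 describes a practice session without dating it. The visit table marks Day 0 as the start of study drug and lists "Distribute study drug" at Visit 1, while Section 8.1.2 labels bottles from Day 1.

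**The case against.** The strongest case against has four parts. First, 0.122 s is not what the plan's model delivers. The plan adjusts for age, so a reader who infers a gain from 0.122 to 0.096 s credits Day 0 with precision that age may already supply. If age explains half of between-subject variance, age alone reaches 0.096 s. This stands, and the comparison has to be made against an age-adjusted model.

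Second, the ICC was set for repeats within one period, not for Day 0 against Days 3–14. Section 7.1 expects worsening followed by non-linear recovery, and enrolment may fall anywhere in the first 72 hours after injury. A weaker correlation is plausible, and this stands as a limit on the gain.

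Third, several passages point to 21 testing days and no Day 0 score. This is not conclusive, because two schedule tables say Days 0–21, but it makes the Day 0 part conditional.

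Fourth, the trial is declared exploratory and no error is shown. That is correct and fixes the weight of the point. It does not remove the case for sex, which rests on the stratified design and not on any uncertain measurement.

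**Conclusion.** The point holds as an optional improvement. The primary model leaves out the factor used to stratify randomisation and gives no role to a Day 0 score. Adding sex aligns the analysis with the design, with a benefit that the documents do not allow one to size. Adding Day 0 would lower the detectable difference by about 0.010 to 0.022 s against an age-adjusted model, for age explaining 50% down to 10% of between-subject variance. That requires a scored pre-dose test in every subject and a Day 0 correlation of 0.5. Weaker correlation or missing scores shrink the gain, and stacked together they bring it close to zero.

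A reader might infer that the power calculation is wrong or that the treatment comparison is biased. Neither follows: 0.122 s reproduces from the stated inputs, and under randomisation the omissions cost precision only.

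**What to change.** 1. Add sex to the primary model alongside age. Cost: one between-subject degree of freedom.
2. Where a scored pre-dose Day 0 CCAT is documented, include it in the primary model. The preferred form treats Day 0 as a response with a common mean across arms, so that subjects without a usable score are kept. Recruitment has begun, so the order of events cannot be set afterwards for subjects already enrolled; Day 0 scores not documented as pre-dose should be treated as missing.
3. State whether a scored Day 0 test, separate from the practice session in Section 6.2.1, is part of the schedule. Reconcile Days 0–21 in Table 1 and Section 5.2 with the 21 time points and Day 1 start in Section 7.3.2, and with the 21-day payment sum in Section 10.7.
4. Reconcile the Day 0 drug start in the Section 5.2 visit table with the bottle labels that begin at Day 1 in Section 8.1.2.

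With 50 subjects, five arms and age, 50 − 5 − 1 = 44 between-subject degrees of freedom remain; 43 or 42 remain after one or both additions. Otherwise the cost is SAP wording, which should be settled before unblinding.

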We note that with five treatment groups and 21 time points, there are a very large number of possible hypothesis tests that can be carried out with these data. If all of these tests were carried out without adjusting for multiple comparisons, we would undoubtedly find spurious associations. On the other hand, adjusting for large numbers of multiple comparisons substantially reduces the statistical power of a study. By focusing our testing for the primary efficacy analysis on three key periods where we adjust for a limited number of tests, we balance the need for a rigorous statistical testing procedure with a need to maintain statistical power.

An analysis of the Day 1-2, 15-18 and 19-21 data will follow the same format, but will be considered secondary and will not be formally corrected for multiple testing. In addition to hypothesis testing, we will estimate and plot means and confidence intervals for each group at each time point. This analysis will guide the recommendation for dose levels and evaluation times for the primary analysis in future efficacy studies.

With concerted efforts from our study coordinators and study staff we are hopeful that we can maintain excellent compliance throughout the study. In particular we expect good compliance early in the study when patients are highly motivated to feel better and return to school, work and play. However, we allow that some patients may have difficulty with compliance due to their injury, or become non-compliant once their symptoms improve. As part of this feasibility study, we will explore patterns of missing data, in particular how they may relate to the observed response (e.g. more missing data in those subjects who show better or worse processing speed) to compliance (e.g. more missing data in subjects who regularly fail to consume their supplements) and to demographics e.g. gender, age. This information will be valuable in planning future efficacy trials, and will guide our efforts to adjust for missing data. For example if the probability of missing data is associated with outcome, then non-ignorable missing data methods will be needed, whereas missing at random assumptions will be valid if the missing data can be explained by covariate information.

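### The three primary global tests use single-step Bonferroni; Holm keeps the same 0.05 family-wise error for those tests and gains power when two or more windows carry an effect, but the gated dose contrasts then need their own stated rule.

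*Combined protocol and SAP*

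**What the plan says.** Section 7.3.2 of the combined protocol and SAP names "three key time periods, Days 3-6, 7-10 and 11-14" as the primary windows. In each, a likelihood ratio test looks for "differences in mean processing speed between placebo and any of the BCAA doses": five groups, so 4 degrees of freedom per window. The three tests are "conducted at a family-wise error rate of 0.05, using a Bonferroni correction to account for the three individual global tests". Each is therefore held at 0.05/3 = 0.0167 whatever the other two show. No step-down is mentioned.

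The global tests are also gates: "If statistical significance is achieved for the global test, we will then compare individual dose levels to placebo within time periods". The plan attaches a multiplicity adjustment to these gated comparisons, "again using a correction for four multiple tests per key time period". The alpha to be divided by four is not given there. Section 7.4 uses a two-sided 0.05 with four contrasts per period, that is 0.0125 each, with no factor for the three windows.

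Section 7.3.2 gives the reason for limiting the tests: "adjusting for large numbers of multiple comparisons substantially reduces the statistical power of a study".

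**The concern.** Once one window is significant at 0.0167, Bonferroni still holds the other two at 0.0167. Holm tests the smallest p-value at 0.05/3, the next at 0.05/2 and the largest at 0.05, stopping at the first failure. It needs no further assumption and no extra data.

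The primary objective (section 3.1) concerns improvement in one or more periods. Section 7.3.2 asks when differences are largest and intends the results to guide evaluation times in later trials. With 10 evaluable subjects per arm, a window missed through an avoidably strict threshold is a real loss. Its dose comparisons are lost with it.

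**Working it through.** **Inputs from the documents.** 10 per group, SD 0.10, ICC 0.5, difference 0.122 s (section 7.4); five equally allocated groups (section 4.2); doses 15, 30, 45 and 54 g/d (section 8.1.3); three windows and family-wise 0.05 (section 7.3.2). Section 7.4 counts three measurements per window, but each window named in 7.3.2 spans four days.

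**Assumptions.** Compound symmetry over all days; effect linear in dose, reaching 0.122 at the top dose, and equal in each active window; F tests on window means standing in for the likelihood ratio tests.

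**1. The plan's own figure.** With three measurements, the SD of a subject's window mean is 0.10 × √((1 + 2 × 0.5)/3) = 0.0816. The standard error of a difference is 0.0816 × √(2/10) = 0.0365. At two-sided 0.0125 the critical value is 2.498, so power = Φ(0.122/0.0365 − 2.498) = 0.80. The stated 80% and N = 50 reproduce. This figure concerns one dose contrast, so the choice between Bonferroni and Holm does not affect it.

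**2. Set-up for the global tests.** With four measurements:
- variance of a window mean: 0.01 × (1 + 3 × 0.5)/4 = 0.00625
- covariance between windows: 0.5 × 0.01 = 0.005
- correlation between windows: 0.005/0.00625 = 0.8
- doses as fractions of 54: 0, 0.278, 0.556, 0.833, 1; sum of squared deviations from their mean 0.658
- noncentrality: 10 × 0.658 × 0.122²/0.00625 = 15.7, on F(4, 45)

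**3. Simulated power, Bonferroni then Holm, correlation 0.8.**

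| Windows with the effect | Power per active window | All active windows declared |
|---|---|---|
| Three | 0.74 → 0.81 | 0.60 → 0.75 |
| Two | 0.74 → 0.77 | 0.65 → 0.71 |
| One | gain about 0.1 point | same |

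With three active windows, power for at least one window is 0.87 under both procedures, because the smallest p-value faces 0.05/3 either way.

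**4. Sensitivity, three active windows.**
- Effect of 0.10 instead of 0.122: all three declared 0.34 → 0.50.
- Correlation 0.5: per window 0.74 → 0.82; all three 0.51 → 0.70.
- Gain in declaring all three: 15 points at correlation 0.8, 19 at 0.5, 23 at 0.
- A different model (known variance, three measurements, 0.122 in one dose only, correlation 0 to 0.75): per window 0.873 → 0.933 to 0.914; all three 0.667 to 0.773 → 0.829 to 0.872. Holm's family-wise error for the three global tests stayed at 0.05 within simulation error (highest 0.0505).

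**5. Effect on the gated contrasts.** Take one dose active in two windows and contrasts at 0.05/12 = 0.0042. Each active window has three true null contrasts; the third window has a true global null.
- Bonferroni bound: 0.0167 + 2 × 3 × 0.0042 = 0.042. Simulated: about 0.03-0.04.
- Holm, when both active windows are rejected: the third is tested at 0.05, so the bound is 0.05 + 0.025 = 0.075. Simulated: about 0.055-0.066.
- Bonferroni with contrasts at the 0.05/4 of section 7.4: bound 0.0167 + 2 × 3 × 0.0125 = 0.092. Simulated: about 0.064-0.080.

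**The case against.** The strongest reply is that Bonferroni is valid, prespecified and simple, and that the gain is largest in the most favourable case. Sections 7.1 and 7.3.2 say the time course is not known, so equal effects in all three windows is an assumption. The objective of section 3.1 is met by one window, and power for that is unchanged. All of this stands, and it limits the size of the point. The plan does, however, expect the largest differences in exactly these three windows and wants to know which they are, so two or three active windows is a scenario it takes seriously.

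The second reply is that Holm has a cost, because the global tests are gates. This also stands. With Bonferroni gates and contrasts at 0.05/12, the 3 global tests and 12 contrasts are jointly bounded by 0.05. Holm passes on a window's alpha while that window's contrasts still use it, and capping each window's contrasts at 0.05/3 in total does not restore joint control. Against this, the plan claims 0.05 for the three global tests only, and with contrasts at 0.05/4 Bonferroni already exceeds 0.05 jointly. Holm therefore breaks no promise the plan makes.

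A reader might also infer that ICC 0.5, through the high correlation between windows, makes Bonferroni especially wasteful here. It does not. The ICC describes subject-level error, not shared treatment effects, and the gain shrinks as correlation rises.

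**Conclusion.** This is a cheap improvement, not the correction of an error. For the three global tests Holm holds 0.05 under any dependence and is never less powerful. Under the linear dose-response assumed above and correlation 0.8, the gain is about 7 points per window and 15 points for declaring all three when all are active, about 3 and 6 points when two are active, and practically nil when one is.

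Two stronger readings are not supported. One is that Holm raises power materially in every key window: that depends on how many windows carry an effect, which the documents do not know. The other is that the change is free: that is true of the global tests alone, but not of the global tests and dose contrasts taken together. The stated 80% power and N = 50 are untouched.

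**What to change.** In section 7.3.2, replace the Bonferroni sentence with one saying that the three global p-values are tested by the Holm procedure at family-wise 0.05 (smallest against 0.05/3, next against 0.05/2, largest against 0.05), and report Holm-adjusted p-values.

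In the same edit, choose one of the following:
- State the alpha for the dose contrasts within each opened window, and state that the 0.05 rate covers the three global tests only.
- If joint control over global tests and contrasts is wanted, prespecify a closed or graphical procedure that includes the contrasts.

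The contrast level also has to agree with section 7.4. At 0.05/4 the 80% stands. At 0.05/12 the same calculation gives 68% at 0.122 s, and the difference detectable with 80% power becomes 0.135 s.

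The cost is a few sentences of SAP wording, settled before treatment codes are opened. No extra subjects or data are needed. The price to record is the higher joint error shown above if the contrasts are left outside the procedure.

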# **3 STUDY OBJECTIVES**

The purpose of this study is to determine whether dietary administration of BCAA's shows evidence of improving the recovery of neurocognitive symptoms after concussion injury, and to determine which of several doses of dietary BCAA's shows the highest promise of efficacy.

8

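### Within a key period, step-down Dunnett would find more of the effective doses than Bonferroni at the same per-period error rate; the per-period level must be stated with it

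*Combined protocol and SAP*

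**What the plan says.** Section 7.3.2 runs three global likelihood ratio tests, one for each key period (Days 3-6, 7-10 and 11-14), at a Bonferroni-adjusted 0.05/3 each. Where a global test is significant, "we will then compare individual dose levels to placebo within time periods, again using a correction for four multiple tests per key time period". That sentence gives neither the method nor the level for the contrasts. Section 7.4 supplies both for the power calculation: a "two-sided family-wise Type I error rate of 0.05 and uses a Bonferroni correction with four contrasts for each time period".

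Section 4.2 allocates subjects equally to the four doses and placebo, so all four contrasts in a period use the same placebo arm. Neither 7.3.2 nor 7.4 mentions Dunnett, Holm or any stepwise method. Section 3 gives as part of the study's purpose "to determine which of several doses of dietary BCAA's shows the highest promise of efficacy", and 7.3.2 says that it wants to keep statistical power while limiting multiplicity.

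**The concern.** Bonferroni treats the four contrasts as if nothing were known about their joint distribution. With equal arms they share the placebo mean and correlate at 0.5, so the true family-wise error within a period falls short of the 5% allowed. Bonferroni also keeps the same critical value for the remaining doses after one has been declared, although fewer null hypotheses can then still be true. Step-down Dunnett uses both facts.

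With 10 evaluable subjects per arm, power cannot easily be recovered by other means. The contrasts feed into the recommendation of doses for later studies, so effective doses missed through an avoidably conservative correction are a real, if modest, loss.

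**Working it through.** **Inputs, all from 7.4 unless noted.** "With 10 subjects per dose group, and three repeated measurements per subject we have 80% power to detect mean differences in processing speeds"; difference "on the order of 0.122 seconds"; SD 0.08, "which we inflated to 0.10"; "The intra-class correlation coefficient was set to 0.5"; four contrasts at two-sided 0.05/4 = 0.0125. Equal allocation is from 4.2, and the global test at 0.05/3 is from 7.3.2.

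**Step 1: reproduce the plan's figure.**
- SD of a three-day mean: 0.10 × √((1 + 2 × 0.5)/3) = 0.0816.
- SE of a difference: 0.0816 × √(2/10) = 0.0365.
- Bonferroni, normal: (2.498 + 0.842) × 0.0365 = 0.1219 s, which is the stated 0.122 s.
- It is not reproduced at 0.05 (0.102 s) or at 0.05/12 (0.135 s). Section 7.4 therefore uses 0.05 per period, divided by four, with no division across the three periods.

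**Step 2: critical values (correlation 0.5, 45 df).** Bonferroni uses 2.60 at every step. Step-down Dunnett uses 2.53, 2.43, 2.28 and 2.01 with 4, 3, 2 and 1 doses remaining. Each is below 2.60, so step-down Dunnett rejects whatever Bonferroni rejects. When no dose works, and before the global test is applied, the within-period family-wise error is 4.2% for Bonferroni and 5.0% for step-down Dunnett.

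**Step 3: 7.4 with Dunnett at the first step, normal basis.** (2.442 + 0.842) × 0.0365 = 0.1199 s. Power at 0.122 s moves from 80.0% to 81.6%. The sample size stays at 10 per arm.

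**Step 4: power of the planned procedure.** Simulation with t on 45 df, true effect 0.122 s in each effective dose, and contrasts counted only if the period's global test passes at 0.05/3 (an F test stands in for the likelihood ratio test). Contrasts are at 0.05 per period:

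| Result | Bonferroni | Step-down Dunnett |
|---|---|---|
| One dose works: found | 71% | 72% |
| Two work: power per dose | 76% | 80% |
| Two work: both found | 64% | 71% |
| Four work: power per dose | 71% | 77% |
| Four work: all found | 51% | 70% |

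**Step 5: where the gain comes from.** Holm steps down but ignores the shared placebo arm. Without the global test, all four doses are found in 51% (Bonferroni), 73% (Holm) and 74% (step-down Dunnett). With one effective dose the figures are 77%, 77% and 79%. Stepping down gives most of the multi-dose gain. The shared arm adds roughly 0.5 to 2 points.

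**Step 6: error across the three periods.** Take one effective dose and three null doses. The effective dose tends to open the contrasts in every period, so up to 3 × 3 = 9 true null contrasts are tested. For Bonferroni at 0.0125 each, the upper bound is 9 × 0.0125 = 11.25%. In simulation, with period means correlated at 0.5/(0.5 + 0.5/3) = 0.75, the chance of any false dose claim is about 7.7% with Bonferroni and 10.5% with step-down Dunnett.

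At 0.05/3 per period the bound for step-down Dunnett is 3 × 0.05/3 = 5% whatever the correlation between periods. The simulated value is 3.8%. At that level finding all four rises from 34% to 54% and finding both of two from 48% to 53%, again with the global test applied.

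**The case against.** - **Bonferroni is valid.** This stands. It controls the error within a period and needs no correlation assumption. A reader might infer that 7.3.2 contains an error; it does not.
- **The swap is not free across periods.** This stands. A reader might infer that Dunnett holds the same error rate at no cost. That is true within a period only. Across the three periods at 0.05 each, the chance of a false claim grows from a figure that already exceeds 5%.
- **The shared placebo arm is not the main reason.** This stands for the multi-dose gains, as the Holm comparison shows.
- **Larger gains can be quoted.** Without the global test, power per dose with four effective doses goes from 77% to 86%. Those are not the powers of the planned procedure, which opens the contrasts only after a significant global test. The largest gains also assume the same 0.122 s effect at every dose.
- **Tests and intervals can disagree.** This stands. The last step rejects at 2.01 while a single-step simultaneous interval uses 2.53. With four effective doses, at least one declared dose had an interval that included zero in 18% of simulated trials with the global test applied.
- **The correlation of 0.5 is a planning value.** This stands in part. Section 4.3.2 stops recruitment at 50 evaluable subjects in total, evaluability requires data only to Day 10, and the model is mixed and age-adjusted. Taking the correlation and degrees of freedom from the fit meets the point.
- **The study is exploratory, and 7.3.2 also plans means and confidence intervals for each group.** This lowers the priority. It does not remove the gain, since formal dose contrasts are still planned.

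**Conclusion.** The point holds as an efficiency improvement within each key period. The gain is about 1 point if one dose works, about 4 points per dose if two work and about 6 points per dose if four work, where finding all four goes from 51% to 70%. The first-step detectable difference moves only from 0.122 to 0.120 s.

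The result assumes normal subject means, equal variances, 10 complete subjects per arm, and three measurements per period as 7.4 counts them. It should be adopted only together with a stated per-period level, because at 0.05 per period it raises the three-period chance of a false dose claim from about 7.7% to 10.5% when one dose works.

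**What to change.** **In 7.3.2:**
- State that, within a key period whose global test is significant, the four dose-placebo contrasts are tested by step-down Dunnett, with correlation and degrees of freedom taken from the fitted mixed model.
- State the per-period level. At 0.05, disclose the three-period error given above. At 0.05/3, the three-period error stays below 5%.
- If single-step Dunnett intervals are reported, say that they may include zero for a dose declared at a later step.

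**In 7.4:** replace Bonferroni with Dunnett and give about 0.120 s on the same normal basis if the level stays at 0.05 per period. If 0.05/3 is chosen, restate the detectable difference for that level. It will be larger; Bonferroni at 0.05/12 gives 0.135 s.

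**Cost:** wording only, with no extra subjects or data, and the method is in standard software. The price of 0.05/3 is power: with step-down Dunnett, finding all four effective doses is 54% at that level against 70% at 0.05.
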